**Study duration and number of study visits required of research participants.**

For the screening portion of the study, each participant will have the following visits: (a) informed consent, (b) PAP run-in phase, and (c) extended-montage sleep study.

After the screening assessments, each participant eligible for randomization will have five visits (randomization, 2 weeks, 1 month, 2 months, and 3 months). To minimize burden, subjects will commence data collection for the CGM and the ambulatory 24 hour blood pressure monitoring at the time of the extended sleep study montage prior to randomization. Finally, because continuous glucose monitoring (CGM) will be conducted for two weeks, participants will exit the study at 3.5 months. During the 2 weeks of CGM, group assignment will remain as at the time of randomization.

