### c. Statistical plan including sample size justification and interim data analysis.

Statistical analyses for the primary evaluation of treatment effects will follow the intention-to-treat paradigm, which means that all randomized patients will be included in the treatment group to which they were assigned. Participants who do not have the requisite data for our primary outcomes will be accounted for and compared by assigned group. Participants not able to be included in the intention-to-treat analyses will be compared to those who are included with respect to demographic and other characteristics. Periodic descriptive summaries of data will be performed to monitor for adverse events and to improve data quality by identifying and investigating outliers in observed measurements.

The primary outcomes for the trial are changes from baseline to 3 months in HbA1c and postprandial hyperglycemia ( $\Delta$ =post-preprandial glucose). Initial analyses will tabulate demographic and baseline characteristics of the participants by randomization group.  $\chi^2$ -tests and one-way ANOVA will be used to compare groups on these characteristics. If differences in some characteristics are observed, even though not statistically significant, these variables will be considered for inclusion in regression models assessing our outcomes. The analytical approach will consist of using mixed model linear regression of the change measure (e.g.,  $\Delta$ HbA1c or improvement in postprandial increment) at 3 months with an indicator variable for the fixed effect for treatment group and baseline value of the measure and adjustment for correlation between baseline and follow-up measures. Additional covariates (e.g., baseline weight and body fat, weight change, sleep duration, activity levels, caloric intake) will be included in the model particularly if the randomization results in serious imbalances in a covariate across treatment groups. More powerful, mixed model repeated measures analyses will also be done using all available longitudinal data on HbA1c and average postprandial-preprandial ( $\Delta$ ) glucose values including rate of change from baseline. The purpose of these analyses is to examine whether the trajectories of our dependent variables vary over time based on the assigned group.

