The secondary outcomes include change in: (1) CGM-derived mean glucose values; (2) systolic, diastolic and mean daytime and nighttime BP; (3) heart rate variability derived indices of sympathovagal balance; (4) endothelial function (Endo-PAT derived reactive hyperemia index); (5) markers of oxidative stress (e.g., oxidized LDL); (6) lipid abnormalities (e.g., LDL, HDL, triglycerides); (7) myocardial injury (troponin-I); and (8) renal injury (urinary albumin and creatinine). All analyses for our secondary outcomes will be done under the intention to treat principle. Initial analyses will tabulate baseline characteristics of participants by randomization group. For our continuous outcomes, we will use multivariable regression and mixed model repeated measures analyses as done for the primary outcomes.

Sample Size Determination:

Sample size was calculated based on the magnitude of anticipated improvement in our primary outcome (e.g., standard deviation [SD] of Dexcom CGM glucose values). The primary assumption for determining sample size was an expected mean decrease in SD of CGM glucose values of 3.3 mg/dl (SD: 6.9 mg/dl) with PAP therapy with no expected change in the control group. Assuming a type 1 error and a power of 90%, a sample size of 92 participants would be needed in each arm (total N=184). To account for modest dropout (~10%), the enrollment goal was 102 participants in PAP therapy arm and 102 participants in the control arm. A total sample size of 184 participants would also allow the study to detect a mean HbA1c difference of 0.36% between the two groups. Enrollment began in December 2014 and ended in December 2019 with a final sample size of 186 participants. In response to the COVID19 pandemic, all clinical research activities ended in early March 2020.

d. Early stopping rules.

Not applicable.

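### Does a final sample size of 186, against an enrollment goal of 204, mean that the plan's 90% power no longer holds?

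*Combined protocol and SAP*

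**What the plan says.** All the figures are in section 7c of the combined protocol and SAP, under Sample Size Determination. The calculation rests on this assumption about the effect: "expected mean decrease in SD of CGM glucose values of 3.3 mg/dl (SD: 6.9 mg/dl) with PAP therapy with no expected change in the control" (so the comparison arm is taken to stay level). From this the plan derives: "Assuming a type 1 error and a power of 90%, a sample size of 92 participants would be needed in each arm (total N=184"). It then allows for losses: "To account for modest dropout (~10%), the enrollment goal was 102 participants in PAP therapy arm and 102 participants in the control arm". A sentence on HbA1c follows: "A total sample size of 184 participants would also allow the study to detect a mean HbA1c difference of 0.36% between the two groups".

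The same paragraph turns from planning to what happened: "Enrollment began in December 2014 and ended in December 2019 with a final sample size of 186 participants". It adds: "In response to the COVID19 pandemic, all clinical research activities ended in early March 2020".

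Two other places bear on the point. In section 4, the part on study duration and visits says that "because continuous glucose monitoring (CGM) will be conducted for two weeks, participants will exit the study at 3.5 months". Earlier in section 7c, the plan commits to this: "Participants who do not have the requisite data for our primary outcomes will be accounted for and compared by assigned group".

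**The concern.** The paragraph holds three totals: 184 needed, 204 to enroll and 186 reached. Since the sentence reporting 186 is about when enrollment opened and closed, its natural comparator is 204, and 186 is 18 short (18/204 = 8.8%). But 186 appears shortly after 184, so a quick reader may conclude that the target was met with two to spare. If 186 is the enrolled number, only two losses (2/186 = 1.1%) are possible before fewer than 184 remain, whereas the plan itself expects about 10%.

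The calendar adds to the worry. Enrollment ran into December 2019, participants stay 3.5 months, and research activity stopped in early March 2020. The last participants randomized may therefore lack the follow-up CGM recording, and CGM is the measure on which the sample size was based. At stake is whether the only power figure in the plan overstates what the trial could deliver.

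**Working it through.** **Inputs.** From section 7c: difference 3.3 mg/dl, SD 6.9 mg/dl, power 90%, 92 per arm, dropout about 10%, goal 102 per arm, 186 reported. Assumption: two-sided alpha 0.05. The plan names a type 1 error without a value.

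**The plan's own figure.** Standardized difference d = 3.3/6.9 = 0.478. Then n per arm = 2 × ((1.960 + 1.282)/0.478)² = 91.87, so 92, as stated. One-sided 0.05 would give 75, so the assumed alpha fits. The allowance of 102 also fits: 92 × 1.10 = 101.2, rounded up to 102 (92/0.90 = 102.2 would give 103).

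**Power if 186 were enrolled.** Power = Φ(d × √(n/2) − 1.960), with n the number per arm with data:

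| Dropout | With data | Per arm | Power (normal) | Power (t-test) |
|---|---|---|---|---|
| 0% | 186 | 93 | 90.3% | 90.0% |
| 5% | 176.7 | 88.35 | 88.9% | 88.5% |
| 10% | 167.4 | 83.7 | 87.2% | 86.8% |
| 15% | 158.1 | 79.05 | 85.2% | 84.8% |
| 20% | 148.8 | 74.4 | 83.1% | 82.6% |

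The first row is also the result if 186 is the number with outcome data. For reference, 92 per arm gives 90.0% (normal) and 89.7% (t-test).

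**Precision at 10% dropout.** The expected 95% half-width for the CGM SD difference goes from 1.96 × 6.9 × √(2/92) = 1.99 to 1.96 × 6.9 × √(2/83.7) = 2.09 mg/dl. The HbA1c difference detectable at unchanged power goes from 0.36% to 0.36 × √(92/83.7) = 0.377%. With 93 per arm it is 0.36 × √(92/93) = 0.358%.

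**Baseline adjustment.** The model in section 7c includes the baseline value, for which the sample size takes no credit. With correlation r between baseline and change, the SD becomes 6.9 × √(1 − r²). The documents give no r. At 83.7 per arm, r = 0.2 gives 88.4% and r = 0.3 gives 90.0%.

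**The March 2020 stop.** Take early March as 1 to 10 March. Counting back 105 days (3.5 months) gives 17 to 26 November 2019, after which the two-week CGM could be incomplete. Counting back 91 days gives 1 to 10 December, after which the 3-month visit could be missing. Accrual was about 186/60 = 3.1 a month, or 3.1 × 12/365 = 0.102 a day. Assuming it was even:

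- 17 or 26 November to 31 December is 45 or 36 days: 4.6 or 3.7 participants.
- 1 or 10 December to 31 December is 31 or 22 days: 3.2 or 2.2 participants.

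That is 2.2/186 = 1.2% to 4.6/186 = 2.5%, inside the 10% allowance.

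**What 186 counts.** The wording points both ways. The sentence opens with enrollment, which suggests people enrolled. Yet the same paragraph uses the term sample size for the numbers before inflation (92 and 184) and calls 102 per arm an enrollment goal. On that usage a final sample size of 186 belongs with 184, not 204.

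**The case for a change.** The best case for a change is that the ambiguity is itself a defect and is cheap to remove. The sponsor holds the counts, and two or three sentences could say what 186 means, how many per arm have 3-month data, and what power or precision results. Until then a reader cannot tell whether 90% describes the trial as it was run. There is also a concrete reason to expect some late losses, and listing the March 2020 stop as its own reason would separate administrative loss from dropout related to treatment.

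Part of this stands. The text does not define 186, and saying what it counts would be a courtesy to the reader. But that is reporting, and it repairs no faulty step in the plan. The losses by arm belong to the accounting that section 7c already promises, where the reason for each loss can naturally be given. Writing a hypothetical 167 participants and 87% power into the plan would be worse than silence, because it would be false if 186 is the number with data. Requests for the alpha value and for the SD and power behind the HbA1c figure are separate matters that do not follow from the gap between 186 and 204.

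**Conclusion.** The concern does not call for a change. The 90% belongs to 184 participants and is correct for that number under a two-sided alpha of 0.05. The HbA1c sentence is likewise tied to 184, not to the number reached.

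A fall to about 87% needs two facts that the documents do not supply: that 186 counts people enrolled, and that a tenth of them were lost. If both held, the cost would be about 3 points of power, 0.10 mg/dl on the half-width and under 0.02 percentage points on the detectable HbA1c difference. A baseline correlation of 0.3, itself an assumption, would bring power back to 90%. If 186 have outcome data, nothing is lost. The March 2020 stop probably affects about 2 to 5 people, assuming even accrual.

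Enrollment is over, so a restated power would alter no decision, model or analysis set, and the confidence intervals will show the precision achieved. This is a gap in reporting that the analysts will fill when they account for participants by arm.

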## 8. Risks

- a. Medical risks, listing all procedures, their major and minor risks and expected frequency.

Questionnaires: There are no risks to completing the study questionnaires.

Actigraphy: There are no risks associated with wearing an Actigraph.

Overnight sleep study: There are no major risks with a sleep study. Rarely, some individuals may experience minor redness or irritation at the site of the monitoring electrodes.

DEXA: This is a widely used test in clinical care for bone density and can also provide measures of body composition. With the newer generation instrument, a whole body scan takes about 6 minutes and the total effective dose of radiation to the participant is 1 millirem. This amount of radiation is significantly less than that from a standard PA + lateral chest x-ray series. Only nonpregnant participants will be enrolled in the protocol.

Anthropometry: There are no risks with anthropometric measurements.

EndoPAT: Risks associated with this test are minor and include numbness, tingling or slight discomfort at the site of the blood pressure cuff during and post inflation. These sensations are temporary and resolve within 2-3 minutes.

Electrocardiogram and Blood Pressure: These are routinely performed in clinical care and have no risks.

Blood Draw: Risks include infection, hematoma, and minor pain at the puncture sites.

PAP Treatment: In our experience with PAP therapy over 20 years, we have not had any serious complications resulting from positive nasal pressure administration in the clinical range ( $\leq 20$  cmH2O). Minor side effects include feeling bloated, nasal mucosal dryness, discomfort from the nasal mask, and irritation of area around the nose where the mask makes contact with the face. Some patients can also develop sinus infections but these are rare and are easily treated.

- b. Steps taken to minimize the risks.

Veni-Puncture: Discomfort, bruise formation, and infection will be minimized by use of sterile supplies and aseptic technique by trained personnel. Any complications will be evaluated by a physician. In the case of an adverse event, the patient will be referred to the appropriate clinical specialist, either outpatient or inpatient for care. Adverse events related to the study procedures will be reported to the IRB. All other procedures (questionnaires, blood pressure monitoring, activity monitoring, SMBG, CGM, sleep study, PAP therapy) are of no more than minimal risk.

- c. Adverse events.

Any adverse events, unanticipated problems or study deviations will be reported to the IRB by the primary investigator. A DSMP plan has been drafted and included in the eIRB application

- d. Legal risks such as the risks that would be associated with breach of confidentiality.

Breach of confidentiality would result in unauthorized individuals having access to information about the participant's medical history. Several different measures will be undertaken to protect participant confidentiality. Paper files will be in locked file cabinets. Access to any computerized information will be restricted to the study investigators or associated staff. Participant data will be stored with unique identifiers and will be password protected. Encryption algorithms that can only be reversed with password access will be implemented. All computers will require log on passwords.
